1 ADMINISTRATIVE INFORMATION

1.1 STUDY IDENTIFIERS

- Protocol: version 4, date 09/03/2021
- ClinicalTrials.gov register Identifier: NCT04454229

1.2 REVISION HISTORY

Version	Date	Details
0.1 (draft)	28/10/2022	First draft by [name]
1.0 (final)	6/11/2022	Updated following review by co-authors
2.0	10/12/2022	Updated the definition of primary outcome which matches ethics approved protocol (misinterpretation in the previous version)

2 STUDY SYNOPSIS

PALACE is a prospective, international, parallel, two-arm, non-inferiority, multicenter randomized control trial evaluating the safety of direct oral challenge vs skin testing prior to oral challenge in adult patients with low-risk penicillin allergy (identified as PEN-FAST <3).¹

The study will test the hypothesis that in an adult population (>18 years) with low-risk penicillin allergy (defined as PEN-FAST score <3), receiving direct oral challenge will be non-inferior to receiving skin testing prior to oral challenge. Non-inferiority will be announced if one sided 95% confidence interval of the risk difference of a positive oral challenge (an immune-mediated reaction) does not exceed 5%.

Given the design of the study, post-randomization events are expected to be minimal – exclusion post-randomization due to ineligibility will be treated using a principal stratum strategy, while all other post-randomization events will be treated using treatment policy strategy.

[■] penicillin unspecified, penicillin VK/G, amoxicillin, ampicillin, dicloxacillin, flucloxacillin

[▲] Skin prick testing followed by intradermal testing using standard beta-lactam panel (Table 1)

2.1 PATIENT POPULATION

The study will be conducted in 6 outpatient clinics in major tertiary centers in Australia (3 sites), Canada (1 site) and US (2 sites).

2.1.1 INCLUSION CRITERIA

- Adult patients referred to the outpatient allergy clinic for a penicillin allergy history.
- Willing and able to give consent.

2.1.2 EXCLUSION CRITERIA

- Age < 18 years.
- PEN-FAST score ≥ 3 .
- Pregnancy.
- Any other illness that, in the investigator's judgment, will substantially increase the risk associated with the subject's participation in this study.
- Patients with a history of type A adverse drug reaction, drug-associated anaphylaxis, idiopathic urticaria/anaphylaxis, mastocytosis, serum sickness, blistering skin eruption or acute interstitial nephritis.
- Patients where the allergy history was not able to be confirmed.
- Patients on concurrent antihistamine therapy.
- Patients receiving more than stress dose steroids (i.e. >50mg QID hydrocortisone [or steroid equivalent]).

2.2 OUTCOMES

2.2.1 PRIMARY OUTCOME

- The difference in the proportion of patients with a positive oral provocation (an immune-mediated reaction) between the intervention and control group.

2.2.2 SECONDARY OUTCOMES

- **Feasibility outcomes:**
 - Proportion of patients referred to the outpatient allergy clinic that are eligible for intervention (i.e randomization) as per protocol [Eligibility to screened ratio]
 - Feasibility of recruitment defined as the proportion of patients consenting to participate in the study as per protocol from eligible patients. [Recruitment to eligibility ratio].
 - Feasibility of intervention delivery defined as the proportion of patients randomized to the intervention arm who had the intervention delivered as per protocol. [Intervention to recruitment ratio]
- **Safety outcomes:**
 - The proportion of patients with a penicillin allergy who experience an antibiotic associated immune mediated adverse event OR severe adverse drug reaction as per protocol definitions within each arm and their difference.
 - The proportion of patients with a penicillin allergy who experience an antibiotic associated non-immune mediated adverse event within each arm and their difference.
 - Protocol compliance within each arm.

- **Efficacy outcomes:**
- Proportion of patients with positive penicillin skin testing within the control arm.
- Proportion of patients with non-immune mediated positive oral challenges within each arm and their difference.
- Proportion of patients with severe adverse reaction within each arm and their difference (serious adverse event is defined as any adverse drug event/experience occurring at any dose that in the opinion of the investigator is causal for any of the following outcomes: death, life-threatening reaction, inpatient hospitalization, persistent or significant disability/incapacity, congenital anomaly/birth defect or requires intervention to prevent permanent impairment or damage).
- Time from randomization to delabelling within each arm and their difference.
- Number of appointments required for penicillin delabelling within each arm and their difference.
- Estimate costs of testing within each arm and their difference.
- Qualitative assessment of the Pre-Questionnaire and 6-month Follow-Up Questionnaire

2.3 INTERVENTION

Intervention: A single dose of oral penicillin, following baseline vital signs (heart rate, blood pressure, respiratory rate).

Control: Routine management as per the treating clinicians that include skin prick and intradermal beta-lactam testing, followed by oral penicillin challenge in the setting of negative skin testing. Vital signs recorded as per intervention group.

2.4 RANDOMISATION AND BLINDING

Permuted block design randomization will be used, stratified by the clinical site. Randomization will be performed via REDCap (Research Electronic Data Capture hosted at Austin Health)² just prior to the intervention. The allocation sequence will be concealed until the time of the randomization. Due to the nature of the control treatment (skin testing) it is impossible to blind study participants, treating clinicians or data collectors. Study investigators (unless they are treating clinicians) will be blinded.

3 STATISTICAL ANALYSIS

3.1 GENERAL PRINCIPLES

While the protocol states that risk differences will be used for analysis of primary and secondary outcome, risk ratios will also be reported. Additional subgroup analysis based on participant age (<65 vs ≥65), sex and reported antibiotic was added. This analysis plan is applicable for all outcomes except cost analysis and 6-month outcomes.

Results will be reported following extension of the CONSORT 2010 guidelines for reporting of noninferiority and equivalence randomized trials³.

Analysis will be conducted primarily using Stata (version 16.1 or above).⁴

3.2 INTERIM ANALYSES

No interim analysis will be performed. Pooled safety outcomes will be presented at regular DSMB meetings.

3.3 MULTIPLICITY ADJUSTMENT

The study has a single primary outcome and its analysis will be unadjusted for multiplicity. One-sided confidence intervals will be used to assess non-inferiority. All secondary outcomes will use two-sided 95% confidence intervals and two-sided tests with a nominal alpha level of 5% if applicable. As most of the secondary outcomes are descriptive and presented for the overall study or within a single arm, no adjustment for multiplicity will be performed.

3.4 DATA SETS TO BE ANALYSED

All analyses will be conducted on an intention-to-treat (ITT) basis. ITT population includes all patients randomized regardless of whether they received the intervention. Any post-randomization exclusions due to ineligibility (expected to be none or minimal) will be excluded from the analysis.

Sensitivity analysis will exclude patients who did not receive intervention as per protocol definitions. Additional sensitivity analysis will include adjustments for the clinical site. This will only be performed for the primary outcome.

3.5 SUBJECT DISPOSITION

Subject disposition will be presented using a CONSORT diagram⁵. This will include the number of patients that were screened, eligible, recruited, randomized and analyzed. Any exclusions will be listed and will include reasons.

3.6 PATIENT CHARACTERISTICS AND BASELINE COMPARISONS

Baseline characteristics will be presented overall and by the treatment group. Continuous variables will be summarized using the median and interquartile range, while categorical variables will be presented using frequencies and percentages.

3.7 COMPLIANCE TO STUDY INTERVENTION(S)

The details of the intervention received will be presented in a table (N and % of patients receiving each type of skin testing and type of oral challenge). The time required to complete the intervention is listed as a secondary outcome.

3.8 ANALYSIS OF THE PRIMARY OUTCOME

Primary analysis will be conducted without missing data imputation, as it is expected that missing data will be minimal. In the event missing data is present in >5% of patients, missing data will be imputed using multiple imputation and imputed data will be used for primary analysis.

3.8.1 MAIN ANALYSIS

Primary endpoint is the proportion of participants experiencing positive oral challenge (immune mediated reaction). Participants with a positive skin test will not undergo oral challenge, therefore will be counted as not achieving primary outcome. Primary analysis will be using generalized linear model (GLM) with binomial family and identity link to estimate the risk difference between intervention and control (reference will be control). This will be presented using a two-sided 90% confidence interval to represent a single-sided 95% confidence interval. If the upper limit of the confidence interval does not cross the non-inferiority margin of 5%, the study will be determined to be non-inferior.

Although clinical site was used as a stratification factor in randomization, adjusting for the site will likely cause convergence issues or produce unstable estimates given the expected small number of outcomes (5% or less) and relatively small number of centres (n=6). Therefore, the main analysis will not adjust for clinical site⁶.

Results will also be presented using risk ratios with two-sided 90% confidence intervals (to represent one-sided 95% confidence intervals), which will be analyzed in the same manner, but using log link. If issues with the model convergence and imputation occur, then GLM with Gaussian family, robust standard errors and identity/log link will be used for risk difference/risk ratio respectively.

3.8.2 SUBGROUP ANALYSES

The following prespecified subgroup analysis will be performed irrespective of the outcome of primary analysis:

1. Clinical immunophenotypes (immediate vs delayed reaction)
2. Number of reported drug allergies (multiple vs single)
3. Immunocompetency (immunosuppressed vs immunocompetent)
4. Age (<65 vs ≥65)
5. Sex (male vs female)
6. Penicillin type (penicillin unspecified vs penicillin VK/G or dicloxacillin or flucloxacillin vs amoxicillin or ampicillin or amoxicillin/clavulanate)
7. Dose of oral challenge drug (250 mg vs 500 mg)
8. Type of skin testing (minor vs major vs Pre-Pen)

Subgroup analysis will be performed by including the subgroup variable and interaction with the

intervention to the GLM model (for subgroups 1-5, no interaction for 6 and 7). The number of events and percentage will be presented for each subgroup, as well as risk difference and risk ratios with 95% confidence intervals. The latter will be presented in forest plot, including p value for interaction.

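### Subgroup 7 uses a challenge dose that skin-test-positive controls never receive, so its between-arm estimates lose control non-events that the main analysis counts

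*SAP*

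**What the plan says.** Section 3.8.2 lists eight prespecified subgroups. Item 7 is "Dose of oral challenge drug (250 mg vs 500 mg"). It stands in the same list as baseline characteristics such as age, sex and number of reported drug allergies. For the list as a whole the section states: "The number of events and percentage will be presented for each subgroup, as well as risk difference and risk ratios with 95% confidence intervals". The estimates go into a forest plot. On the model, the section gives interactions "for subgroups 1-5, no interaction for 6 and 7".

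Four other places bear on item 7:

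- Section 2.4: randomisation takes place "just prior to the intervention", and "it is impossible to blind study participants, treating clinicians or data collectors".
- Section 2.3: controls have an oral challenge only if skin testing is negative.
- Section 3.8.1: "Participants with a positive skin test will not undergo oral challenge, therefore will be counted as not achieving primary outcome".
- Section 3.4: all analyses follow intention to treat, on all randomised patients apart from those found ineligible.

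The SAP does not say who sets the dose, when or on what basis. It also does not say where patients without a dose go in the item 7 analysis.

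**The concern.** A subgroup comparison keeps the protection of randomisation only if the subgroup variable is defined for everyone and cannot be affected by allocation. Dose received fails the first condition by design. A patient who is never challenged belongs neither to the 250 mg row nor to the 500 mg row, and a positive skin test can remove patients in this way from the control arm only. The dose analysis would therefore set direct-challenge patients against controls who have already passed a skin test. The main analysis sets them against all controls.

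Every control removed by a positive skin test is a non-event under section 3.8.1. The direction is therefore fixed: the control rate can only rise, and the risk difference can only move in favour of direct challenge. The row for item 7 would stand in one forest plot with valid baseline subgroups, with nothing to show that it rests on a different and non-randomised comparison.

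**Working it through.** **Inputs from the SAP.** Section 2.5 gives 190 per group, a 4% control event rate, a 5-point margin, one-sided 5% error and 80% power. Sections 2.3 and 3.8.1 establish that skin-test-positive controls have no challenge and count as non-events.

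**Assumptions.** The SAP gives no skin-test positivity rate; I take s = 2%, 4% and 10% of controls. I take p, the share of all randomised controls who react at challenge, as 4%.

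**The plan's own figure.** With the unpooled variance formula, n per arm = (1.645 + 0.842)² × (2 × 0.04 × 0.96) / 0.05² = 6.183 × 0.0768 / 0.0025 = 189.9. This rounds up to 190, or 380 in total, as stated. No number in the SAP is disputed here; this only confirms the 4% and the 190 as working inputs.

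**Step 1: who drops out.** Controls without a dose because of a positive skin test number 190 × s, which is 3.8, 7.6 or 19. No intervention patient is lost for this reason.

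**Step 2: effect on the control rate.** In the main analysis the rate is p. Among challenged controls it is p / (1 − s), so the shift is p × s / (1 − s).

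| s | Main analysis | Challenged controls only | Shift (points) |
|---|---|---|---|
| 2% | 4.00% | 0.04 / 0.98 = 4.08% | 0.08 |
| 4% | 4.00% | 0.04 / 0.96 = 4.17% | 0.17 |
| 10% | 4.00% | 0.04 / 0.90 = 4.44% | 0.44 |

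These are shifts over the two dose levels together. A true risk difference of zero would appear as about −0.1 to −0.4 points.

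**Step 3: sensitivity to the meaning of the 4%.** Section 2.5 words its hypothesis in terms of a positive oral challenge or skin test, whereas section 3.8.1 counts oral challenge reactions only. If the 4% includes skin-test positives, then p = 4% − s. At s = 2% the shift is 0.02 × 0.02 / 0.98 = 0.04 points, which is about its maximum; at s = 4% it is zero. The shift also shrinks if skin testing catches true reactors. With p = 2% and s = 10% it is 0.02 × 0.10 / 0.90 = 0.22 points.

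**Step 4: does the model form matter?** With an interaction, each dose row omits the undosed controls. Without one, the model gives a single arm effect adjusted for dose plus a dose effect, and it is still fitted only to patients who have a dose. The loss of controls is the same either way. If the promised risk difference is read instead as 250 mg against 500 mg, that contrast was not randomised at all.

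**The case against.** The strongest reply is that the SAP already sets item 7 apart by giving it no interaction. That stands in part. A model without an interaction produces neither a separate arm effect at each dose nor a p value for a dose-by-arm pattern. It does not restore the missing controls, and it does not fit the promise of a risk difference for each subgroup.

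A reader might go further and infer that unblinded clinicians steer dose by perceived risk, differently in the two arms, and so create a false dose-by-arm pattern of several points. The SAP does not support this. Section 2.4 says that clinicians are unblinded, not that they choose the dose. The dose rule may lie in the protocol, and a dose fixed by site would be known before randomisation. Any figure for such steering would rest on invented risk splits and steering rates, so it remains a possibility without a size. Section 3.7 does not settle the matter either: it tabulates "N and % of patients receiving each type of skin testing and type of oral challenge" and does not mention dose.

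A reader might also infer that the trial's non-inferiority claim is at risk. It is not. That decision rests on the main analysis in section 3.8.1, and the subgroups carry no non-inferiority test, so the 5-point margin is not the yardstick for item 7.

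Finally, the shift is small beside the imprecision. With an assumed 95 patients per arm at each dose and 4% rates, the 95% half-width is 1.96 × √(2 × 0.04 × 0.96 / 95) = 5.6 points. This is true and limits the weight of the point. It does not make the comparison a randomised one.

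**Conclusion.** The point holds in a limited form. Dose received is undefined for skin-test-positive controls, so a between-arm estimate using it discards non-events from one arm only and departs from the intention-to-treat rule in section 3.4. This follows from the SAP's text and needs no assumption about how dose is set.

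The size does depend on assumptions: about 0.1 to 0.4 points in favour of direct challenge if 4% of all controls react at challenge and 2% to 10% are skin-test positive, and less if the 4% includes skin-test positives. Lack of comparability through arm-dependent dose choice is possible but cannot be established or sized from the SAP. The primary estimate, the sample size and the non-inferiority conclusion are unaffected. Separately, the promise of a risk difference for each subgroup and the absence of an interaction for item 7 need to be reconciled. The matter is one of validity and labelling, worth correcting before analysis because correction costs almost nothing.

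**What to change.** Remove item 7 from the between-arm subgroup list and from the forest plot in section 3.8.2. Report reactions by dose received as counts and percentages within each arm, among challenged patients, labelled descriptive and non-randomised. Removing the item also settles, for item 7, the mismatch between a risk difference for each subgroup and a model without an interaction.

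If the dose is fixed before randomisation, for example by site, item 7 can stay on a different definition: use that pre-randomisation value as the subgroup variable, assign it to every randomised patient including skin-test-positive controls, and state whether an interaction is fitted.

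The cost is SAP wording only. The downside is that no between-arm estimate by dose received is shown.

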3.8.3 TREATMENT OF MISSING DATA

Missing data is expected to be minimal and if present in <5%, no missing data imputation will be performed. If the missing data will be present in >5%, then multiple imputation stratified by randomization group will be performed using logistic regression model with at least 50 data sets imputed⁷. The results will be combined to obtain a pooled risk difference and risk ratio.

3.8.4 OTHER SENSITIVITY ANALYSES

Sensitivity analysis will include adjustment for clinical site and per-protocol analysis.

3.9 ANALYSIS OF SECONDARY OUTCOMES

3.9.1 FEASIBILITY OUTCOMES

All feasibility outcomes will be presented using percentage with exact two-sided 95% confidence intervals.

3.9.2 SAFETY and EFFICACY OUTCOMES

All safety and binary efficacy outcomes will be presented as counts (percentage) within each arm and comparison between arms will be same as for the main outcome (using GLM model to evaluate risk difference and risk ratio, both presented with two-sided 95% confidence intervals).

Continuous efficacy outcome (time from randomization to delabelling) will be presented as mean (SD) or median (IQR). Linear regression will be used for comparison between arms. Results will be presented as mean difference with 95% confidence intervals. Homoscedasticity of residuals will be inspected visually and if violated then outcome will be transformed using natural logarithm.

Count outcomes (number of appointments required) will be analyzed using negative binomial regression with outcome expressed as incidence rate ratio with 2-sided 95% confidence intervals. If the variability in the number of appointments required will be minimal, the outcome will be transformed into a binary variable (1 appointment vs multiple appointments) and analysis will be performed using GLM, results reported as risk difference and risk ratio with two-sided 95% confidence intervals.

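### SAP 3.9.2 gives severe adverse reactions the primary-outcome GLM, whose Wald-type intervals fail when an arm has few or no events, and sets no sparse-data rule

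*SAP*

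**What the plan says.** SAP 2.2.2 lists severe reactions twice. One safety outcome is a composite: "antibiotic associated immune mediated adverse event OR severe adverse drug reaction as per protocol definitions within each arm and their difference". A separate item, placed under efficacy, is "Proportion of patients with severe adverse reaction within each arm and their difference".

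SAP 3.9.2 sets the method for both. Within arms, "All safety and binary efficacy outcomes will be presented as counts (percentage) within each arm", with no within-arm interval. Between arms, "comparison between arms will be same as for the main outcome (using GLM model to evaluate risk difference and risk ratio". As to the intervals for these two measures, the section has them "both presented with two-sided 95% confidence intervals".

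The model itself is defined in SAP 3.8.1: "Primary analysis will be using generalized linear model (GLM) with binomial family and identity link to estimate the risk difference". The risk ratio is obtained by a model "which will be analyzed in the same manner, but using log link". If convergence problems arise, "GLM with Gaussian family, robust standard errors and identity/log link will be used for risk difference/risk ratio respectively".

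The SAP has no rule for an arm without events and no exact or score interval for safety outcomes. Exact intervals are specified only for the feasibility outcomes (3.9.1).

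**The concern.** The method in 3.8.1 was chosen for a primary outcome assumed to occur in about 4% of controls. Section 3.9.2 carries it over to an outcome that is probably much rarer: reactions that are fatal, life-threatening, lead to admission or are of similar gravity, in patients with PEN-FAST below 3 and after several high-risk histories are excluded. The models named in the SAP derive a standard error from the observed proportions, and an observed proportion of zero has an estimated variance of zero.

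At stake is what the report says about serious harm. No events in 190 patients is compatible with a true risk of almost 2%. An interval that is too narrow or has no width hides this. If the software stops instead, no analysis is prespecified and one has to be chosen after the data are seen.

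**Working it through.** **Inputs.** 190 per arm (SAP 2.5). Two-sided 95% intervals, z = 1.96 (SAP 3.9.2). The severe-reaction rate r is not stated, so 0.1% to 1% is assumed.

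**Step 1: the plan's own figure.** With 4% in both arms, margin 5%, one-sided 5% and 80% power, n = (1.645 + 0.842)² × 2 × 0.04 × 0.96 / 0.05² ≈ 190 per group. The stated size reproduces.

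**Step 2: how often an arm is empty.** P(one given arm empty) = (1 − r)^190. P(both) = (1 − r)^380. P(at least one) = 1 − [1 − (1 − r)^190]².

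| Assumed r | Given arm empty | At least one empty | Both empty |
|---|---|---|---|
| 0.1% | 83% | 97% | 68% |
| 0.25% | 62% | 86% | 39% |
| 0.5% | 39% | 62% | 15% |
| 1% | 15% | 27% | 2% |

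For comparison, at the 4% assumed for the primary outcome in controls, a given arm is empty with probability 0.96^190 = 0.04%. The problem does not carry over to the primary analysis.

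**Step 3: risk difference, 0 v 0.** The Wald standard error is √[p₁(1 − p₁)/190 + p₂(1 − p₂)/190] = 0.
- In statsmodels, the binomial identity model gave a standard error of about 1.5 × 10⁻⁹.
- A linear model with robust (HC1) errors gave exactly 0 to 0.
- The Gaussian GLM routine stopped with an error.
- Newcombe: the Wilson upper limit for 0/190 is z²/(190 + z²) = 3.84/193.84 = 1.98%, so the interval is -1.98% to +1.98%. Miettinen-Nurminen gives -1.99% to +1.99%.
- Exact upper limit for one arm: 1 − 0.025^(1/190) = 1.92%.

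**Step 4: risk difference, one empty arm.** For 2 v 0 the difference is 2/190 = 1.05%.
- Wald: SE = √(0.01053 × 0.98947/190) = 0.74%, so the interval is -0.40% to 2.50%. The binomial identity model converged to this result, and the Gaussian model with robust errors gave the same.
- Newcombe: the Wilson limits for 2/190 are 0.29% and 3.76%. Lower limit = 1.05 − √[(1.05 − 0.29)² + 1.98²] = -1.07%. Upper limit = 1.05 + (3.76 − 1.05) = 3.76%.
- Miettinen-Nurminen: -0.94% to 3.76%.

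For 1 v 0 the SAP model gives -0.50% to 1.56%, against -1.50% to 2.92% by Newcombe.

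**Step 5: risk ratio, one empty arm.** The likelihood keeps rising as the empty arm's fitted risk goes to zero, so no finite estimate exists. For 1 v 0 the binomial log model stopped at a log risk ratio of about 20 with a standard error of about 14,000. The Gaussian log fallback printed ratios from about 2.4 × 10⁵ to 1.8 × 10⁷ depending only on the convergence tolerance. Each came with a finite interval far from 1 (for example 3.4 × 10⁴ to 1.7 × 10⁶).

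**Step 6: coverage of the nominal 95% Wald interval.** Binomial probabilities were summed over all outcomes whose interval contains the true difference. At assumed true rates of 0.5% v 0.1%, coverage is about 67%. Most of the shortfall is the 0 v 0 case, which has probability 0.386 × 0.827 = 32% and always misses the true difference of 0.4%. At 1% v 0.25%, coverage is about 85%. When the true rates are equal, a 0-to-0 interval happens to contain the true difference, and coverage is not short (99% at 0.5% in both arms). The failure therefore appears when the arms really differ.

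**The case against.** The case on the other side has several parts.

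- **The low rate is not in the SAP.** This stands. A reader might infer that the plan itself expects almost no severe reactions. Its only stated expectation, 5% or less in 3.8.1, is for the primary outcome. The low-risk population and the exclusions make a low rate plausible, but at 1% both arms are empty only 2% of the time.
- **The fallback is not the cause.** This stands for the risk difference with one empty arm. A reader might blame the Gaussian robust-error step, but the main binomial identity model converges there and gives the same narrow interval. Dropping the fallback alone would change nothing.
- **A printed 0-to-0 interval is not certain.** This stands. One might infer that the plan must report a difference of 0.0% with limits of 0.0 and 0.0. The variance is algebraically zero, but one routine stopped with an error, and Stata, which SAP 3.1 names, was not tested.
- **Scope is limited.** This stands. The composite safety outcome includes immune-mediated events and should rarely be empty. No non-inferiority decision rests on the severe-reaction interval.
- **Counts are shown anyway.** True, and a reader would see 0/190 v 0/190. But no within-arm interval goes with them, so the only interval on offer would be the defective one.
- **With 2 v 0 both methods include zero.** True, but a safety interval is read for the largest excess it leaves open: 2.5% under the SAP model, 3.8% by Newcombe.

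**Conclusion.** The point holds, mainly for the stand-alone severe adverse reaction outcome. The cause is the Wald-type interval of the GLM in general, in the main model and the fallback alike. At 190 per arm and an assumed rate of 0.5% or less in each arm, an empty arm is more likely than not (62% or more).

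The method as written then gives one of three results: a degenerate interval or an error for 0 v 0; an interval too narrow by roughly one percentage point at the upper end for 1 v 0 or 2 v 0; or a risk ratio without meaning. This is more than a missing detail, because 3.9.2 does fix a method and it fails in a likely case.

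The documents do not support going further, to say that all safety results or the non-inferiority conclusion are compromised. The size of the problem rests on the assumed rates, and the software behaviour on statsmodels.

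**What to change.** In SAP 3.9.2, for severe adverse reaction and any other sparse binary safety outcome:

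- Report each arm's proportion with an exact (Clopper-Pearson) 95% interval, as 3.9.1 already does for feasibility.
- Report the risk difference with one prespecified score-type 95% interval, Newcombe or Miettinen-Nurminen, replacing both the GLM Wald interval and its Gaussian fallback.
- Report the risk ratio as not estimable when an arm has no events.

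Naming the outcomes in advance avoids a cut-off for sparse. If a cut-off is preferred, it is a convention that the SAP must state before the data are seen.

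The cost is a sentence or two in the SAP and standard methods. Safety intervals become wider, and at these rates the score-type interval is conservative. The primary analysis and its conclusion do not change.

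### Time to delabelling is compared without clinical site, the randomisation stratum, for a reason that does not fit a continuous outcome; if site is prognostic, its 95% interval is wider than it need be

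*SAP*

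**What the plan says.** SAP 2.4 sets the allocation scheme: "Permuted block design randomization will be used, stratified by the clinical site". There are six clinics in three countries (2.1), and the control arm receives "Routine management as per the treating clinicians", including skin testing before any oral challenge (2.3).

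For the primary outcome, 3.8.1 considers site and sets it aside: "Therefore, the main analysis will not adjust for clinical site". The ground given is that, with an event rate of at most 5% and six centres, a site term would probably fail to converge or give unstable estimates. Section 3.4 then limits where site may appear at all: "Additional sensitivity analysis will include adjustments for the clinical site. This will only be performed for the primary outcome". Section 3.8.4 repeats the site sensitivity analysis, but inside the primary-outcome section.

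For time to delabelling, 3.9.2 says "Linear regression will be used for comparison between arms", with the result given as a mean difference and 95% interval, and a log transformation if the residuals are heteroscedastic. No covariate is named and no separate reason is given for omitting site. Number of appointments is to be analysed by negative binomial regression, or by a binary model (one versus several appointments) if the counts hardly vary.

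**The concern.** Stratified blocks balance site between the arms, so differences between sites add almost nothing to the sampling error of the arm difference. An arm-only regression nevertheless puts those differences into the residual variance and so into the standard error. The point estimate barely changes, but the reported interval is wider than the design warrants. The usual remedy is to include the stratification factor.

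The SAP's reason for not doing so concerns a rare binary outcome. It does not reach a least-squares model with five extra indicators, yet 3.4 rules out even a sensitivity analysis with site for this outcome. A site effect is plausible, since time to delabelling depends partly on how a clinic organises testing. At stake is how precisely the trial can report a difference in speed between the two pathways.

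**Working it through.** **Inputs from the SAP.** 380 patients, 190 per arm (2.5); six sites (2.1); permuted blocks within site (2.4); two-sided 95% intervals for secondary outcomes (3.3).

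**Assumptions, not in the SAP.** R², the share of outcome variance due to site (range 0 to 0.50); blocks of 4; site sizes (near-equal in step 2, 100/80/70/60/40/30 in step 3).

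**1. The plan's own figure.** The SAP gives none for this outcome. Its sample size for the primary outcome does reproduce. With 4% in both arms, a 5% margin, one-sided 5% and 80% power, n per arm = 2 × 0.04 × 0.96 × (1.645 + 0.842)² / 0.05² ≈ 190. Here it only supplies the 380.

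**2. Site effects common to both arms.** With total variance 1, the arm-only residual variance is 1 and the site-adjusted one is 1 − R². The width ratio, unadjusted over adjusted, is therefore 1/√(1 − R²). For example, at R² = 0.20 it is 1/√0.80 = 1.118. Simulation with no arm effect (4,000 trials per row) gave:

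| R² (assumed) | Formula | Simulated ratio | Unadjusted coverage | Adjusted coverage |
|---|---|---|---|---|
| 0 | 1.000 | 1.000 | 94.7% | 94.8% |
| 0.05 | 1.026 | 1.026 | 95.7% | 95.1% |
| 0.10 | 1.054 | 1.054 | 95.9% | 95.0% |
| 0.20 | 1.118 | 1.118 | 97.6% | 95.3% |
| 0.30 | 1.195 | 1.196 | 98.4% | 95.4% |
| 0.50 | 1.414 | 1.416 | 99.4% | 95.0% |

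The simulation error of a coverage figure is √(0.95 × 0.05 / 4000) ≈ 0.3 percentage points, so the first row is consistent with 95%.

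**3. Site effects in the control arm only.** Let s be the site share of control-arm variance, with residual variance 1 − s in both arms.
- The arm-only residual variance averages (1 − s) + s/2 = 1 − 0.5s.
- A common site term removes half of each site's control-arm shift and leaves s/4, giving 1 − 0.75s.
- The adjusted-to-unadjusted width ratio is √[(1 − 0.75s)/(1 − 0.5s)].

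At s = 0.10, 0.20, 0.40 and 0.50 this is 0.987, 0.972, 0.935 and 0.913. Simulation (2,000 trials) agreed, with intervals about 1%, 3%, 6% and 9% narrower. Coverage was about 96–98.5% unadjusted and 96–98% adjusted, so adjustment does not fully restore 95% here.

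**4. Number of appointments.** Counts were simulated as 1 + Poisson(extra visits), with mean extra visits running from 0.05 up to 1.0 across sites. They were fitted in the Poisson limit of the negative binomial, because the counts are underdispersed. The width ratio was 1.00 and coverage about 100%, with or without site. Those intervals are wide because the model's variance cannot fall below its mean, and a site term does not change that.

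Under the binary fallback, the ratio was 1.00 with equal site rates. With site rates of 2%, 5%, 10%, 20%, 40% and 60% it was 1.15 (coverage 97.5% unadjusted, 95.0% adjusted).

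**5. Cost.** Residual degrees of freedom fall from 380 − 2 = 378 to 380 − 7 = 373.

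**The case against.** The case against acting is substantial, and parts of it stand.

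- **The loss is conditional.** A reader might infer that the interval is too wide in any event. The SAP gives no between-site variance, and at R² = 0 nothing is lost. Randomisation takes place just before the intervention, and the primary outcome is collected at the same visit (2.4, 2.5), which may limit how far clinic organisation drives the timing. This stands.
- **The mechanism may sit in one arm.** The SAP's clearest pointer to site variation is that control care follows the treating clinicians. If sites differ only there, step 3 applies and the gain is small. This stands.
- **Number of appointments.** A reader might extend the point to this outcome. The documents do not support that: step 4 shows no narrowing under the planned negative binomial model, and 3.9.2 already foresees a binary fallback. If few patients need a second visit, the few-events concern returns. Whether a rate ratio is the right effect measure is a separate question.
- **No validity is lost.** A reader might infer wrong conclusions or false positives. The unadjusted interval is conservative, the outcome is secondary and was not powered, and 3.3 calls most secondary outcomes descriptive.
- **Not every patient contributes.** A patient with a positive skin test has no oral challenge (3.8.1), so time to delabelling is not plainly defined for everyone. The analysed number may be below 380, but not by enough to make five site indicators a difficulty if positive tests are as uncommon as 2.5 assumes.

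None of this supplies a reason for omitting site from the regression for time. The only reason in the SAP concerns a rare binary outcome.

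**Conclusion.** The point holds for time to delabelling as a matter of precision. The model omits the stratification factor, 3.4 excludes it even from sensitivity analysis, and the SAP's stated ground does not apply to a continuous outcome.

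The size depends on an assumed site share of variance. With effects common to both arms, the unadjusted interval is wider by about 3% at a 5% share, 5% at 10%, 12% at 20% and 42% at 50%. With effects in the control arm only, the adjusted interval is about 1% to 9% narrower for shares of 10% to 50%. With no site effect the difference is nil. Coverage of the planned interval stays at or above 95%, within simulation error. No such claim is made for number of appointments.

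**What to change.** In 3.9.2, add clinical site (six levels, fixed effect) to the linear regression for time to delabelling, on the original or the log scale, and report the site-adjusted arm difference as the main result. In 3.4, lift the restriction of site adjustment to the primary outcome for this outcome.

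For number of appointments, include site only where the model converges and events are not sparse, without expecting the negative binomial interval to narrow.

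The cost is a few words in two sections and five degrees of freedom. The change should be made before the outcome data are compared by arm.
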